BoExp to nicotine NEQ, Total NNAL, Total NNN, and CEMA will serve as indicators of overall exposure of the patients throughout the study. These markers have relatively long half-lives, and should provide a good estimate of the exposure, even if the patient comes early in the morning for his/her visit. Because nicotine is expected to be delivered with IQOS at levels comparable to CC, levels of NEQ are not expected to be lower in IQOS users than CC users, but it will serve as an overall estimate of exposure to nicotine exposure. Levels of Total NNAL and Total NNN as tobacco-specific nitrosamines are expected to be significantly reduced in IQOS users compared to CC smokers, close to what is expected when patients stop smoking. Urinary excretion of CEMA, a biomarker of acrylonitrile which is generated as an incomplete combustion product in CC, is expected to be higher in smokers than in non-smokers and IQOS users. Additionally, CEMA levels in smokers are significantly correlated with ISO tar yield, daily CC consumption, and other urinary BoExp. Spot-urine collection will be performed, and the BoExp levels will be adjusted to creatinine to adjust urinary excretion rates.

The exclusion of patients with a diagnosis of concomitant genetic diseases such as Marfan syndrome, Loeys-Dietz syndrome, Vascular Ehlers-Danlos syndrome, Turner syndrome, Polycystic kidney disease, Noonan syndrome, Alagile syndrome, Arterial tortuosity syndrome and Cutis laxa is based on the fact that these diseases significantly affect occurrence, location and clinical course of AAA development and progression and would therefore not allow a clear assessment of the effect of smoking, SC or switching to IQOS on AAA growth rate.

This study is designed as an *ad libitum* study without product use restriction in order to mimic as closely as possible “real life” conditions.

All patients will be asked to buy their own CC or *HeatSticks*, according to their needs for the study, in order to minimize any changes in their smoking behavior, and to not promote one product over the other. As different brands of commercially available and/or roll-your-own CC will be used, neither the nicotine content of each CC is predefined nor the maximum as well as the minimum of the CC nicotine content is limited.

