9.1.5 Handling of Dropouts or Missing Data

For BoExp parameters:

- Values below the lower limit of quantification (LLOQ) will be imputed using LLOQ/2. For values above the upper limit of quantification (ULOQ), the ULOQ will be imputed.
- The number and percentage of values below LLOQ or above ULOQ will be presented in each summary table (the percentage of values below LLOQ/ULOQ will use the number of patients with non-missing values in the denominator). If more than 50% of the data are below LLOQ, only the number and percentage of values below LLOQ will be reported in the summary together with the minimum and maximum values.

For self-reported tobacco or nicotine-containing product use:

- Only available data will be included in the product use summaries.

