9.5.2.2 Cardiovascular Risk Factors Biomarker of Exposure

Summary of Cardiovascular Risk Factors		
Population	:	FAS
Group	:	
• Study Arm• Product Use Category
Contents	:	
• Refer to Descriptive statistics• Calculate the value of Cardiovascular Risk Factors for each visit. Also, calculate the change from baseline.
Analysis variables	:	
• Systolic blood pressure• Diastolic blood pressure• Body weight• Waist circumference
Target visit		Baseline (V2) to V8
Output		Summary of Cardiovascular Risk Factors -FAS- Summary of Cardiovascular Risk Factors by Product Use Category - FAS- Series plot of Cardiovascular Risk Factors -FAS- Series plot of Cardiovascular Risk Factors by Product Use Category - FAS- Listing of Cardiovascular Risk Factors

Summary Table of Analysis for BoExp Geometric Mean Value		
Population	:	FAS
Group	:	
• Study Arm• Product Use Category
	:	
• The analysis will be performed on the FAS using a mixed model for repeated measurements (MMRM).• The model will include the log transformed BoExp adjusted for creatinine as the dependent variable, adjusting for the following covariates;

Confidentiality Statement

Data and information contained in this document are considered to constitute trade secrets and confidential commercial information, and the legal protections provided to such trade secrets and confidential information are hereby claimed under the provisions of applicable law. No part of this document may be publicly disclosed without the written consent of Philip Morris Products S.A

Summary Table of Analysis for BoExp Geometric Mean Value

	
➤ Study Arm or Product Use Category➤ log(BoExp value at V2)➤ Visit➤ Interaction between visit and Study Arm or Product Use Category• Degree of freedom will be adjusted by using KR.• Number of patients included in analysis, Geometric LS means (IQOS-CIG), Ratio of Geometric LS Means and 95% CI for Ratio of Geometric LS means at each visit for each product use will be presented.• Select Unstructured (UN) specified for the correlation structure. If the model fails to converge try following option in order; a first order autoregressive (AR(1)), Compound Symmetry (CS), and uncorrelated (IND).

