Analysis variables	
• NEQ adjusted for creatinine• Total NNAL adjusted for creatinine• Total NNN adjusted for creatinine• 2-CyEMA adjusted for creatinine
Target visit	: V3 to V8
Sample code	<pre>proc mixed data=test ; class ARM VISIT ; model Log(AVAL) = ARM Log(Base) VISIT ARM * VISIT / s cl ddfm=kr; repeated VISIT / type=un subject=USUBJID ; lsmeans ARM * VISIT / diff=control("CIG" "1") cl ; ods output diffs=diff ; ods output lsmeans=lsmean ; ods output convergencestatus=check ; run;</pre>
Output	Summary of Analysis for BoExp Geometric Mean Value -FAS- Summary of Analysis for BoExp Geometric Mean Value by Product Use Category -FAS-

Confidentiality Statement

Data and information contained in this document are considered to constitute trade secrets and confidential commercial information, and the legal protections provided to such trade secrets and confidential information are hereby claimed under the provisions of applicable law. No part of this document may be publicly disclosed without the written consent of Philip Morris Products S.A.

Summary Table of Analysis for BoExp Geometric Mean Value

	
Time Series Plot of Geometric LS Mean Biomarkers of Exposure Parameters -FAS-
 
Time Series Plot of Geometric LS Mean Biomarkers of Exposure Parameters by Product Use Category -FAS-
 
Listing of Statistical Output (MIXED procedure)
 
Listing of Statistical Output (MIXED procedure) by Product Use Category

--	---

Summary Table of BoExp Parameters

Population	:	FAS
Group	:	
• Study Arm• Product Use Category
Contents	:	In addition to the descriptive statistics of value and change from baseline for each visit, the number and percentage of values below LLOQ or above ULOQ will be presented. If more than 50% of the data are below LLOQ, only the number and percentage of values below LLOQ will be reported in the summary together with the minimum and maximum values. In addition, the geometric means, CV and geometric relative change will be presented.
Analysis variables	:	
• NEQ adjusted for creatinine• Total NNAL adjusted for creatinine• Total NNN adjusted for creatinine• 2-CyEMA adjusted for creatinine• Creatinine (Only on listing)
Target visit		Baseline (V2) to V8
Output		Summary of Biomarkers of Exposure Parameters -FAS- Summary of Biomarkers of Exposure Parameters by Product Use Category -FAS- Listing of Biomarkers of Exposure Parameters

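### The biomarker MMRM has no stated rule for values below LLOQ, so a ratio and 95% CI can be reported where the SAP's 50% rule would limit the summary to counts

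*SAP*

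**What the plan says.** SAP 9.1.5, for all BoExp parameters, sets the imputation: "Values below the lower limit of quantification (LLOQ) will be imputed using LLOQ/2". It adds a disclosure rule, "The number and percentage of values below LLOQ or above ULOQ will be presented in each summary table", and a reporting limit: "If more than 50% of the data are below LLOQ, only the number and percentage of values below LLOQ will be reported", together with the minimum and maximum. Protocol 12.1.4 has the same imputation and the same 50% limit.

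SAP 9.5.2.2 specifies the model: "The model will include the log transformed BoExp adjusted for creatinine as the dependent variable". The sample code is "model Log(AVAL) = ARM Log(Base) VISIT ARM * VISIT", fitted to NEQ, Total NNAL, Total NNN and 2-CyEMA at V3 to V8, by study arm and again by product use category. The output is "Ratio of Geometric LS Means and 95% CI for Ratio of Geometric LS means at each visit for each product use will be presented". Neither this specification nor protocol 12.7 mentions an LLOQ threshold, an exclusion, a censored likelihood or a sensitivity analysis.

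The descriptive BoExp table in the same SAP section repeats the 50% rule, then adds without condition: "In addition, the geometric means, CV and geometric relative change will be presented".

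SAP 5.1.1 divides each biomarker by spot-urine creatinine. Protocol 4.1 expects Total NNAL and Total NNN in IQOS users to be "close to what is expected when patients stop smoking", CEMA to be higher in smokers than in IQOS users, and NEQ not to be lower with IQOS than with cigarettes.

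**The concern.** The 50% rule treats a mean built mostly on imputed values as not worth reporting. The same imputed values then enter the MMRM, which reports a geometric LS mean, a ratio and a 95% CI from them. One report could therefore withhold a mean in one table and give a ratio from the same data in the next.

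The imputed values also carry little information. If LLOQ/2 is imputed on the measured concentration before creatinine division (the natural order, though the SAP does not state it), a censored sample enters as (LLOQ/2)/creatinine. That varies only with urine dilution. As censoring rises, the group mean settles near half the assay limit, whatever the true exposure.

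This can reach the randomised contrast. By the protocol's own expectation, the IQOS arm may be heavily censored for Total NNAL and Total NNN, and possibly for 2-CyEMA. The IQOS product use category and the SC arm are more exposed still. The IQOS/CIG ratio for NEQ is not at risk.

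**Working it through.** **Inputs from the documents.** LLOQ/2 imputation, the 50% limit and 95% CIs (SAP 9.1.5 and 9.1.8); log(BoExp/creatinine) as response (SAP 9.5.2.2); 1:1 randomisation (SAP 4.3.1.1); 32 patients enrolled in total when recruitment was stopped (protocol 4.4). The documents state no LLOQ, SD, expected percentage below LLOQ or arm sizes, so there is no plan figure to reproduce.

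**Assumed inputs.** Log SD of exposure 0.8; log SD of creatinine 0.5; 10 patients per randomised arm and 12 in SC; CIG geometric mean 20 × LLOQ; SC geometric mean 0.1 × LLOQ where SC is included.

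**Step 1: percentage below LLOQ.** With true IQOS/CIG ratio r, the IQOS geometric mean is 20r × LLOQ. The log concentration has SD √(0.8² + 0.5²) = 0.943, so

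p = Φ(−ln(20r)/0.943).

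For r = 0.020: 20r = 0.4, −ln 0.4 = 0.916, 0.916/0.943 = 0.971, p = 83%. For r = 0.0125: 20r = 0.25, 1.386/0.943 = 1.47, p = 93%.

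**Step 2: the floor.** If every IQOS value is censored and creatinine is balanced, the ratio becomes (LLOQ/2)/(20 × LLOQ) = 0.025 for any true r.

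**Step 3: simulation.** This is a single-visit analogue of the visit contrast: impute LLOQ/2, divide by creatinine, take logs, and compare arms with a pooled variance.

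| True ratio | % of IQOS below LLOQ | Reported ratio | Coverage of 95% CI, without SC | Coverage, SC in pooled variance |
|---|---|---|---|---|
| 0.100 | 23 | 0.097 | 95% | 91% |
| 0.050 | 50 | 0.052 | 95% | 91% |
| 0.040 | 59 | about 0.043 | 95% | 91% |
| 0.030 | 71 | about 0.037 | 91% | 87% |
| 0.020 | 83 | 0.030 | 74% | 67% |
| 0.0125 | 93 | 0.027 | 31% | 24% |

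True IQOS and SC levels of 0.4 and 0.1 × LLOQ (ratio 4) appear as about 0.61 and 0.50 × LLOQ (ratio 1.2).

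**Step 4: other assumptions.** With log SD 1, log creatinine SD 0.6, 12 per arm and LLOQ at 10% of the CIG mean, coverage is about 95% at 50% below LLOQ, 81% at 72% (0.05 reported as 0.074) and 18% at 92% (0.02 reported as about 0.055). At the same SDs, moving the LLOQ through 5%, 10% and 20% of the CIG mean changes the reported value of a true 0.01 from 0.028 to 0.051 to 0.101, so the assay limit sets the result.

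Without dilution, the factor on the IQOS geometric mean has a closed form, with s the log SD:

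exp{s[p·z_p + φ(z_p)] − p·ln 2}.

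For s = 0.5 / 1.0 / 1.5 it is 0.86 / 1.05 / 1.29 at p = 50%, 0.90 / 1.35 / 2.05 at 75% and 1.04 / 2.02 / 3.93 at 90%. The error can thus go downward when spread is small and censoring moderate, but it is upward under heavy censoring in every case shown.

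**The case against.** **The rule may already cover the model.** It stands under general BoExp handling and limits what appears in the summary, and the MMRM output is itself titled a summary table. That reading is possible. But SAP 9.5.2.2 repeats the rule only for the descriptive table, promises a model ratio at every visit, and nowhere says whether the 50% is counted by arm, visit or biomarker. On either reading the model is still fitted to the LLOQ/2 values. What does not stand is the stronger reading that the SAP forbids a mean above 50%: it only says what will be reported.

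**The trigger is unknown.** This stands. No LLOQ, SD or expected percentage is given. The arm analysis also keeps dual users in their randomised arm, and the protocol anticipates dual use (12.3), which would raise IQOS-arm levels. The exposure is therefore clearer for the IQOS product use category than for the randomised arm.

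**Little happens at 50%, and the error is mostly conservative.** Both stand. At 50 to 60% below LLOQ the ratio is nearly unbiased. A ratio of 0.030 for 0.020 means a 97% instead of a 98% reduction. A reader might infer that the imputation flatters IQOS against cigarettes; under heavy censoring it does the opposite. The apparent closeness of IQOS to SC is a separate matter. No IQOS/SC ratio is planned, but the LS-mean plots are produced by study arm.

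**Censoring is disclosed.** The descriptive table gives the number and percentage below LLOQ. That helps the reader but does not correct the CI beside the model ratio.

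**Conclusion.** The point holds as a conditional gap. The MMRM has no stated condition for heavy censoring, and its ratios and CIs can be driven by the assay limit and urine dilution if most values in a group are below LLOQ. Under the assumed inputs, harm is negligible up to about 60% below LLOQ, moderate near 70% and serious from roughly 80% (coverage 74% at 83%, 31% at 93%). These figures rest on assumed SDs, arm sizes and LLOQ, and on a single-visit comparison without the baseline covariate or repeated measures.

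A reader might go further and infer that the IQOS ratios will be wrong. The documents do not support that, because they do not show that any group will pass 50%. A reader might also infer that taking SC out of the model cures the problem. It does not: the 74% and 31% are already without SC, whose effect on the pooled variance is a separate issue.

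The endpoints are secondary and descriptive with no hypothesis tested, and the primary AAA growth analysis is untouched. The change should be made because it is cheap and removes an inconsistency within the SAP.

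**What to change.** In SAP 9.5.2.2, state that the 50% rule applies to the MMRM geometric LS means and ratios, counted per biomarker, group (study arm or product use category) and visit. Where a group exceeds 50%, report neither its estimate nor any ratio that uses it; give the number and percentage below LLOQ with the minimum and maximum.

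In the descriptive BoExp table, make the sentence on geometric means, CV and relative change subject to the same rule.

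Optional: a left-censored model on concentration, with log creatinine as offset, as a sensitivity analysis where enough values are quantified. In an illustrative fit (log SD 1, 12 per arm) it returned 0.057 for a true 0.05 at 72% below LLOQ, against 0.074 with LLOQ/2. At about 90% below LLOQ most simulated data sets had fewer than two quantified values and it was not usable, so it cannot replace the reporting rule.

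The cost is a few sentences in the SAP, a flag in the output programs, and some visit ratios that will not be reported. The sensitivity model would need extra programming.

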9.1.5.1 Insufficient Data for Analysis/Presentation

If no data is available for presentation for a TFL, then a blank TFL will be displayed with “No applicable data for this summary.” displayed.

9.1.6 Handling of Unplanned Data

All data collected on scheduled visits will be used for tables. Therefore, data collected on unscheduled visit will be excluded from tables, however included in listings (no time window will be considered).

Confidentiality Statement

Data and information contained in this document are considered to constitute trade secrets and confidential commercial information, and the legal protections provided to such trade secrets and confidential information are hereby claimed under the provisions of applicable law. No part of this document may be publicly disclosed without the written consent of Philip Morris Products S.A

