Each month during the Investigational Period, patients will complete a questionnaire on self-reported current tobacco and nicotine-containing product consumption (including frequency and quantity of product use) over the past month.

At every visit during the Investigational Period, spot urine and blood samples will be collected. CT scans and further assessments will be performed according to the schedule of events (Appendix 1). Following the end of their Investigational Period, the patients will be discharged from the study.

At V8, any non-serious AE that is ongoing after completion of discharge procedures at Visit 8 will be documented as “ongoing”. At that point, the Investigator will assess whether the patient should be referred to his/her General Practitioner for further follow-up on their ongoing AEs. All SAEs will be followed up by the Investigator until resolution, stabilization (i.e., no worsening of the condition), or until an acceptable explanation has been found (e.g., a chronic condition).

Unscheduled visits:

As a general rule, procedures requested in the protocol should be performed according to the visit schedule. However, as this study is focused on treating patients, there may be a number of reasons that the patient may visit the investigational site outside of the visit schedule during the course of the study. The site should record any site visit and document the reason for the visit and the assessments performed during the unscheduled site visit.

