8.4.2 Reporting other abnormal findings

The other abnormal findings discovered during different clinical assessments (e.g., ECG, physical examination, vital signs) should be evaluated for the clinical significance by the Investigator/designee based on his/her medical judgement. All abnormal clinical significant test results or clinical examination findings can, at the discretion of the Investigator, be reported as AEs.

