8.6 Adverse Events Leading to Discontinuation

Patients who are discontinued from the study because of an AE will undergo the early termination procedure, as described in Section 9.4, as soon as possible. The Investigator will follow-up these AEs as described in Section 8.2.2.

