9.4 Early Termination Procedures

For patients who terminate the study early, the procedure of discharge planned for V8 will be performed as an early termination (Table 7).

Table 7 Time Schedule – Early Termination Procedures

Time	Sample collection	Procedures	Additional Information
Start of Procedure			
During the visit		Advice on the risks of smoking/SC advice Follow-up on concomitant diseases (ongoing or not)	
During the visit	U	Spot urine collection for pregnancy	Pregnancy test (all females, except when menopause is confirmed): at the study site
	B/U	Blood/Urine: Hematology, clinical chemistry, urine analysis Clinical assessments: Electrocardiogram Physical examinations	Blood samples have to be taken after at least 10 hours of fasting. At least 5 minutes in supine position

Confidentiality Statement

Data and information contained in this document are considered to constitute trade secrets and confidential commercial information, and the legal protections provided to such trade secrets and confidential information are hereby claimed under the applicable provisions of applicable law. No part of this document may be publicly disclosed without the written consent of Philip Morris Products S.A.

End of the visit	Return of IQOS device AE/SAE/product event recording	For IQOS arm only upon early discontinuation
------------------	---	---

Abbreviations: AE = Adverse event; SAE = Serious adverse event.

If the patient withdraws from the study, or is discontinued based on Investigator judgment, he/she will be asked to perform the early termination procedure as soon as possible after the time of discontinuation unless the patient refuses to do so (section 5.2).

Confidentiality Statement

Data and information contained in this document are considered to constitute trade secrets and confidential commercial information, and the legal protections provided to such trade secrets and confidential information are hereby claimed under the applicable provisions of applicable law. No part of this document may be publicly disclosed without the written consent of Philip Morris Products S.A.

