9.5.4.3 Clinical Laboratory Evaluation

Laboratory Evaluation	
Population	: Safety Set
Group	: Study Arm
Contents	
• Refer to Descriptive statistics• Calculate the value of laboratory parameters for each visit. Also, calculate the change from baseline.
➢ Clinical chemistry➢ Hematology• Also create a graph displaying mean ± standard deviation.• For parameters with the reference range, calculate the number and percentage of subjects in low, normal, or high compared to the reference range.• For urine analysis, calculate the number of subjects in each visit and the number of subjects in each result category by visits.
Analysis variable	: Create for the following categories 
• Clinical chemistry• Hematology• Urine analysis
Output	: Summary of Laboratory Parameters -Safety Set- Summary of Abnormal Laboratory Parameters -Safety Set-

Confidentiality Statement

Data and information contained in this document are considered to constitute trade secrets and confidential commercial information, and the legal protections provided to such trade secrets and confidential information are hereby claimed under the provisions of applicable law. No part of this document may be publicly disclosed without the written consent of Philip Morris Products S.A.

	Series plot of Laboratory Parameters -Safety Set- Summary of Qualitative Urine Parameters -Safety Set- Listing of Laboratory
--	--

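### Abnormality counts for laboratory tests, ECG and physical examination omit unscheduled-visit results, and the SAP does not say where early-termination results go

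*SAP*

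**What the plan says.** SAP 9.1.6 sets one general rule for all tables. It first says "All data collected on scheduled visits will be used for tables", then that "data collected on unscheduled visit will be excluded from tables, however included in listings (no time window will be considered". There is no exception for safety data.

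The SAP's safety sections then describe these summaries:

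- **Laboratory (9.5.4.3):** values and changes from baseline for each visit; for parameters with a reference range, "calculate the number and percentage of subjects in low, normal, or high compared to the reference range".
- **Physical examination (9.5.4.4.3) and ECG (9.5.4.4.5):** numbers of subjects in each result category, by visit.
- **Vital signs (9.5.4.4.4):** values and changes from baseline for each visit.

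None of these sections mentions a worst value or an any-post-baseline count.

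The protocol expects results from outside the regular visits. For unscheduled visits, section 4 says "The site should record any site visit and document the reason for the visit and the assessments performed during the unscheduled site visit". For patients who leave early, section 9.4 says "the procedure of discharge planned for V8 will be performed as an early termination", and its Table 7 lists blood and urine safety tests, ECG and physical examination. Section 8.6 adds that "Patients who are discontinued from the study because of an AE will undergo the early termination procedure".

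Protocol 12.8 promises the number and percentage of Safety Set patients with clinical findings for laboratory parameters, ECG, physical examination and vital signs. It also promises shift tables from baseline for ECG, physical examination and laboratory parameters.

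**The concern.** A safety abnormality count should answer a patient-level question: how many patients in each arm had an abnormal result at any time after baseline? Under the SAP as written, a patient whose only abnormal result was found at an unscheduled visit is not counted in any laboratory, ECG or physical-examination table.

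Early-termination results have a different problem. They are required by protocol, but the SAP gives them no place. A programmer would have to choose between dropping them and assigning them to a visit. The obvious candidate is V8, because the protocol models the exit procedure on the V8 discharge. That would put a result from a patient who left after a few months under the 36-month heading.

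At stake is how complete the descriptive safety summaries under secondary objective 4 are, in a study small enough for single patients to change an arm's percentage visibly.

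**Working it through.** The plan states no figure on this point and its sample size is not based on a hypothesis, so there is nothing to reproduce. The check is a comparison of sections, followed by an illustration of scale.

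**1. Unscheduled results.** SAP 9.1.6 removes them from tables and rules out visit windowing, so they cannot re-enter through a neighbouring visit. The low/normal/high laboratory count does not itself say that it is by visit. Even read as an any-time count, it would still exclude unscheduled results, because 9.1.6 applies to all tables.

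**2. Early-termination results.** Three places in the SAP could have settled their assignment:

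- 9.1.6 speaks only of unscheduled visits. Protocol section 4 describes those separately from the early-termination procedure of 9.4.
- 9.1.5, on dropouts and missing data, covers only biomarkers of exposure and product use.
- 5.7 has a rule for early terminators, but only for the product-use average.

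The protocol's schedule of events (Appendix 1) has no early-termination column, so the assignment is undefined. ECG shows the consequence most clearly. After baseline it is scheduled only at V4, V6 and V8 (Protocol 7.5.1). If exit results were dropped, a patient who left before V4 would have no post-baseline ECG in any table, although Table 7 requires one. If they were mapped to V8, that ECG would appear at month 36.

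**3. Against Protocol 12.8.** The promised count of patients with clinical findings is not restricted to scheduled visits. SAP 9.5.4 names no shift table, and SAP section 7, which lists changes from the protocol analyses, does not record the omission.

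**4. Scale, by assumption.** Inputs from Protocol 4.4: 32 patients enrolled, and 15 more forecast as potentially eligible. The documents give no numbers per arm, so I assume an equal split over three arms.

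- 32 / 3 = 10.7, about 11 per arm. One patient is 100 / 11 = 9.1 percentage points.
- (32 + 15) / 3 = 47 / 3 = 15.7, about 16 per arm. One patient is 100 / 16 = 6.25, about 6 percentage points.

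If the only affected patient in an arm is omitted (Clopper-Pearson 95% intervals):

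| Patients per arm | With the patient counted | As tabulated |
|---|---|---|
| 11 | 1/11 = 9.1% (0.2 to 41.3%) | 0/11 = 0% (0 to 28.5%) |
| 16 | 1/16 = 6.25% (0.2 to 30.2%) | 0/16 = 0% (0 to 20.6%) |

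This is simply 1/n. It shows what one omission does, not how often omissions would occur.

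**The case against.** The strongest reply is that harm is mainly captured elsewhere. Protocol 12.8 makes AEs the primary safety assessment, and SAP 9.5.4.1 counts them over the study period, not by visit. Protocol 8.4.1 requires clinically significant laboratory abnormalities found after screening to be recorded as AEs or linked to a concomitant disease or a reported AE. Protocol 7.5.1 requires a diagnosis on the CRF for each clinically relevant abnormal ECG. Unscheduled results stay in the listings, which can be read patient by patient in a study of this size. Table layouts sit in a separate shell document that is not available here, so the absence of a row can be stated only of the SAP text.

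Much of this stands. It narrows the consequence, but a listing gives no count by arm, and an AE table counts events judged reportable, not patients with abnormal results. The separate shells do not override the general rule in 9.1.6.

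A reader might go on to infer more than the documents support:

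- **That early-termination results are excluded.** 9.1.6 does not name them and no section calls that visit unscheduled. The finding is silence.
- **That ECG and physical-examination findings become AEs only if the investigator chooses.** Protocol 8.4.2 does say "All abnormal clinical significant test results or clinical examination findings can, at the discretion of the Investigator, be reported as AEs", but 8.2.2.2 says without that qualification that new clinically relevant abnormal findings will be documented as AEs. The two passages must be reconciled.
- **That every safety table is by visit.** AE, device-event, medical-history and medication tables are not.

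**Conclusion.** The point holds within limits. By the explicit rule in SAP 9.1.6, an abnormality found only at an unscheduled visit is missing from the laboratory, ECG and physical-examination counts. No planned any-post-baseline count recovers it, and the handling of early-termination results is unspecified. The AE tables offset this in part but do not deliver the patient-level findings count or the shift tables of Protocol 12.8.

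The number of patients affected cannot be derived from the documents. The 9-point and 6-point figures rest on the assumed equal split of 32 or 47 patients and describe one omitted patient only.

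It is tempting to conclude that the tables would understate harm more in the arm with more AE-driven exits, and so make that arm look safer. The documents do not support this. Section 4 gives only unspecified reasons for unscheduled visits. Early-termination procedures are not confined to safety exits: discontinuation reasons in Protocol 5.2.1 also include withdrawn consent and site closure. Nothing indicates that exits would differ by arm. The direction of any distortion is unknown.

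**What to change.** - **SAP 9.1.6:** limit the exclusion of unscheduled data to by-visit summaries.
- **SAP 9.5.4.3, 9.5.4.4.3 and 9.5.4.4.5:** add for each arm an any-post-baseline row (worst category per patient) that uses scheduled, unscheduled and early-termination results.
- **SAP 9.5.4.4.4 (vital signs):** the same row would add unscheduled results only, because Table 7 does not list vital signs. The SAP would first have to state what counts as a finding, since this section plans only values and changes.
- **Early termination:** state that these results enter the any-post-baseline row and are not placed in the V8 column.
- **Consistency:** either provide the shift tables of Protocol 12.8 or record their omission in SAP section 7, and reconcile Protocol 8.2.2.2 with 8.4.2.

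The cost is SAP wording and a row in existing tables, from data already collected. If the database is already locked, SAP section 1 allows supplementary analyses described in the clinical study report. The downside is that patients tested more often have more chances to show an abnormality, so the by-visit rows should stay alongside the new one.
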